8.2.6 Flowchart

All visits and data collections are outlined below in [Table 8–1](#).

Table 8–1 Flow chart of study-related data collection

Study NN1250-4189	Planning to initiate	Initiation	Observation period			
			V3 ¹	V4 ¹	V5 ¹	V6 ¹
Visit Number (V)	V1 ¹	V2 ¹	V3 ¹	V4 ¹	V5 ¹	V6 ¹
Time of visit (Months)	-1	0	3	6	9	12
Visit window (days)		+14	±45	±45	±45	±45
PATIENT RELATED INFO/ASSESSMENTS						
Informed consent	X					
In/Exclusion criteria	X	X				
Initiation		X				
Withdrawal criteria		X	X	X	X	X
Demographic data	X					
Height, systolic and diastolic blood pressure (if available)	X					
Body weight (if available)	X	X	X	X	X	X
Diagnosis of diabetes	X					
Insulin use – is the patient a high dose insulin user (>80 U/day)	X					
Hypoglycaemia risk: is the patient prone to hypoglycaemia	X					
Concomitant ill/ medical history	X					
Anti-diabetic treatment type and dose ²	X	X	X	X	X	X
Concomitant medications	X	X	X	X	X	X
Reason for switching or not switching to Tresiba [®]		X				
First date on study insulin (Tresiba [®])		X				

Study NN1250-4189	Planning to initiate	Initiation	Observation period			
SAFETY AND EFFECTIVENESS						
Distribution and collection of patient diaries ³	X	X	X	X	X	X
Most recent FPG and date of measurement (if available)	X	X	X	X	X	X
Most recent HbA _{1c} and date of measurement (if available)	X	X	X	X	X	X
Total daily dose of bolus insulin on day prior to visit (if applicable)		X	X	X	X	X
Changes in any social, leisure and working activities due to insulin treatment		X	X	X	X	X
SADRs, MESI and pregnancies ⁴		X	X	X	X	X
Hypoglycaemic episodes ⁵	X	X	X	X	X	X
PRO questionnaires ⁶ : SF-36 (version 2) DTSQ ⁷	X	X	X	X	X	X
Patient preference			X	X	X	X
End of study						X ⁸

Abbreviations: DTSQ=diabetes treatment satisfaction questionnaire; FPG=fasting plasma glucose; HbA_{1c}=glycated haemoglobin A1c; MESI=medical events of special interest; SADR=serious adverse drug reaction; PRO=patient reported outcomes; SF-36=Short form-36; V=visit.

¹ Decision to initiate the study will take place 4 weeks prior to actual initiation of Tresiba[®] treatment, and with this a statement reported by the physician that use of current medication (for 4 weeks) will not be a safety problem for the patient. Patient material will be handed out at visit 1 to explain the importance of the baseline reporting period. It is not guaranteed that all patients will attend all visits.

² For anti-diabetic treatment also collect the insulin dosing regimen.

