8.4.1 Patient diaries

Upon providing informed consent, each patient will be given a study diary and provided guidance in its use. There will be 2 diaries, the first one will cover 4 weeks of baseline data (between visits 1 and 2) and the second one will cover the 4 weeks prior to each physician visit (visits 3 to 6). At the visit following completion of the diary, the patient will return his/her diary and will be given a new one. Data from the diary will be entered into the eCRF. The diary will be kept in the source files at the investigational site.

The 4-week diaries will include sections for information such as:

- Insulin dose and time of administration
- Details of missed doses and dose-time flexibility
- Number of SMBG test strips used
- Information related to hypoglycaemic episodes. Each time the patient has a symptom of hypoglycaemia or his/her blood sugar level is below or equal to 3.9 mmol/L (70 mg/dL), the patients will be encouraged to complete the diary (exact time, PG value, assistance required or not)
- Resource use due to hypoglycaemia.

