8.4.3 Visit 1 Physician plans to initiate Tresiba[®] (Week -4)

The patient will receive complete information about the study both orally and in writing. Informed consent must be given prior to any trial-related data being collected.

The visit will include:

- Signature of informed consent and recording of the date informed consent was given
- Determination of eligibility by checking the inclusion/exclusion criteria (Section [8.2.2](#) and Section [8.2.3](#)). The decision as to which T1DM and T2DM patients will start Tresiba[®] treatment is determined by the treating physician
- Distribution of all PROs to be completed by the patient. This will be done prior to any following steps. The questionnaires will be administered while the subject is in the waiting room or another dedicated room
- Demography – collecting age, sex, ethnicity
- Blood pressure (systolic and diastolic) and height measurements, if available
- Body weight (kg), if available
- Medical history
- Physician will document if the patient is hypo-prone
- Concomitant medications (related to diabetes - including insulin dosing regimen)
- Physician will document if the patient is a high dose insulin user (>80 U/day)
- Collection of the most recent HbA1c and FPG and date of the measurements
- Patients will be interviewed and asked to recall any severe hypoglycaemic episodes in the 6 months prior to this visit
- Distribution of diary and guidance on use.

The patient will be instructed to:

- Continue on current therapy, as prescribed by the physician and lifestyle interventions
- Record in the diary every episode of hypoglycaemia occurring over the following 4 weeks
- Record in the diary insulin dose, time, and date (over the following 4 weeks)
- Record in the diary if any doses are missed and what the patient did
- Record in the diary how many SMBG strips they use over the following 4 weeks
- Record in the diary any resource use due to hypoglycaemia over the following 4 weeks
- Bring the diary to the next clinical visit.

An appointment will be made for their next usual clinical visit (visit 2, initiation) in approximately 4 weeks (+14 days).

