8.4.4 Visit 2, Initiation/Baseline (Month 0)

The decision to treat patients is entirely based on the physician's decision in accordance with local practice.

This visit will include:

- Check of inclusion, exclusion and withdrawal criteria (see Sections [8.2.2](#), [8.2.3](#) and [8.2.4](#))
- Distribution of all PRO questionnaires to be completed by the patient. This will be done prior to any following steps
- Body weight (kg), if available
- Concomitant medications, including current insulin dosing regimen, will be recorded
- Collection of the most recent HbA1c and FPG and date of the measurements
- Collection of safety information. Patients will be asked about any AEs as part of standard care. Each SADR, severe hypoglycaemic episode (regardless of physician's evaluation of seriousness and causality), MESI, and pregnancies will be recorded on a separate AE form and SIF according to existing reporting procedures and timelines
- Collection of diary and distribution of a new one
- The patient will be asked what their total daily dose of bolus insulin was on the day prior to the visit, if applicable
- The patient will be asked if their insulin treatment required them to change any social, leisure, and working time activities
- Physician will document the reason for switching or not switching to Tresiba[®] treatment as applicable
- Based on physician decision, patients will commence treatment on Tresiba[®]

The patient will be instructed to:

- Continue on current therapy including Tresiba[®], as prescribed by the physician and lifestyle interventions
- Record in the diary every episode of hypoglycaemia occurring over the 4 weeks prior to the next visit
- Record in the diary insulin dose, time, and date (for 4 weeks prior to the next visit)
- Record in the diary if any doses are missed and what the patient did, and details of dose-time flexibility
- Record in the diary how many SMBG strips they used over the 4 weeks prior to the next visit
- Record in the diary any resource use due to hypoglycaemia over the 4 weeks prior to the next visit
- Bring the diary to the next clinical visit.

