8.4.5 Observation period (standard routine visits)

The time window for visits 3, 4, 5, and 6 (Months 3, 6, 9, and 12) are ± 45 days. Visits are based on the regularity of visits to a treating physician under normal clinical management of a diabetic patient.

These visits will include:

- Patients will be assessed to determine if they meet any of the withdrawal criteria (Section [8.2.4](#)).
- Distribution of all PRO questionnaires to be completed by the patient. This will be done prior to any following steps. The questionnaires will be administered while the subject is in the waiting room or another dedicated room.
- Body weight (kg), if available.
- Collection of the most recent HbA1c and FPG and date of the measurements.
- The patient will be asked what their total daily dose of bolus insulin was on the day prior to the visit, if applicable.
- The patient will be asked if their insulin treatment required them to change any social, leisure, and working time activities.
- Concomitant medications, including current insulin dosing regimen, will be recorded
- Collection of safety information. Patients will be asked about any AEs as part of standard care. Each SADR, severe hypoglycaemic episode (regardless of physician's evaluation of seriousness and causality), MESI, and pregnancies will be recorded on a separate AE form and SIF according to existing reporting procedures and timelines.
- Collection of diary (at all visits) and distribution of a new one at visits 3, 4 and 5 only.

- Patients will be asked their preference for Tresiba[®] or their previous treatment.

The patient will be instructed to (except for the end of study visit 6, Month 12):

- Continue on current therapy including Tresiba[®], as prescribed by the physician and lifestyle interventions
- Record in the diary every episode of hypoglycaemia occurring over the 4 weeks prior to the next visit
- Record in the diary insulin dose, time, and date (for 4 weeks prior to the next visit)
- Record in the diary if any doses are missed and what the patient did, and details of dose-time flexibility
- Record in the diary how many SMBG strips they used over the 4 weeks prior to the next visit
- Record in the diary any resource use due to hypoglycaemia over the 4 weeks prior to the next visit
- Bring the diary to the next clinical visit.

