8.5 Study size

The sample size calculation is based on the primary observational endpoint, which is the change from the baseline period (4-week baseline period) in the number of any hypoglycaemic episodes occurring during the 12-month observation period with Tresiba[®]. The change from baseline measure is operationalised as the mean of the per-patient paired differences in hypoglycaemic episodes/PYE.

For both T1DM and T2DM, the mean of paired differences is expected to be 1 episode/PYE with a standard deviation of 7 (a conservative estimate based on our understanding of possible variation in the measures). At $\alpha=0.05$ and 90% power, the number of patients who switch to Tresiba[®] and complete the 12-month observation period is $n_{T1DM}=n_{T2DM}= 517$. Assuming a 15% rate of withdrawal (loss of patient for any reason prior to completing 12-month observation period), 608 T1DM and 608 T2DM patients will need to be enrolled and complete the 4-week baseline period and switch to Tresiba[®] to achieve 517 T1DM and 517 T2DM patients completing the observation period.

The data from the participating countries will be pooled. Analysis on data from the patients in Germany up to the discontinuation date will be specified in the SAP.

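### The protocol describes emphasis on why recording matters for the baseline diary only, leaving an unacknowledged risk that less complete on-Tresiba diaries would read as a fall in hypoglycaemia

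*Protocol*

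**What the plan says.** Footnote 1 to the flow chart (Protocol 8.2.6, Table 8-1) states: "Patient material will be handed out at visit 1 to explain the importance of the baseline reporting period". No corresponding material is described for the four diaries kept on Tresiba.

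Section 8.4.1 ties diary guidance to consent: "Upon providing informed consent, each patient will be given a study diary and provided guidance in its use". The visit 1 list (8.4.3) has the matching item, "Distribution of diary and guidance on use". The visit 2 list (8.4.4) has the old diary collected and a new one given out, without mentioning guidance. For later visits, 8.4.5 says "Collection of diary (at all visits) and distribution of a new one at visits 3, 4 and 5 only", again without guidance.

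The instruction itself is repeated. At visit 1 the patient is told: "Record in the diary every episode of hypoglycaemia occurring over the following 4 weeks". At visit 2 it is: "Record in the diary every episode of hypoglycaemia occurring over the 4 weeks prior to the next visit". Section 8.4.5 repeats the visit 2 form for the remaining diaries.

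Section 8.5 sizes the study on this expectation: "the mean of paired differences is expected to be 1 episode/PYE with a standard deviation of 7".

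**The concern.** The comparison is valid only if a patient is about equally likely to write down an episode in both periods. Several features make the count sensitive to effort. Section 8.3.2.1 counts a measured plasma glucose of 3.9 mmol/L or below even without symptoms, so the count depends on testing and recording as well as on events. Section 8.4.1 encourages diary completion rather than requiring it. There is no concurrent group in which a drift in recording would show.

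If patients are told why the baseline diary matters and are not told the same about the later ones, recording may weaken after the switch. Fewer recorded episodes with no true change would look like a fall in hypoglycaemia, which favours the product on its primary safety endpoint.

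The limitations in 8.9 do not cover this. They treat heavier monitoring at baseline as something that may affect glucose control and the decision to switch. They discuss bias in the change from baseline through a baseline rate that is too low, which would make a benefit harder to show. They say that a prospective diary limits error and missing data, without separating the two periods. The checklist in Annex 2 (item 7.1.2) answers No on information biases.

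**Working it through.** **Step 1: the two sides of the contrast, as described.**

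| | Baseline diary (visit 1 to 2) | On-Tresiba diaries (before visits 3 to 6) |
|---|---|---|
| Material on why reporting matters | Described (8.2.6, footnote 1) | None described |
| Guidance on diary use | Listed at consent and visit 1 (8.4.1, 8.4.3) | Not listed again (8.4.4, 8.4.5) |
| Instruction to record every episode | Yes (8.4.3) | Yes, near-identical (8.4.4, 8.4.5) |

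The asymmetry is in explanation and guidance, not in the instruction.

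**Step 2: reproduce the plan's own figure.** Inputs from 8.5 and 8.7.2.2: difference 1 episode/PYE, SD of paired differences 7, two-sided alpha 0.05, power 90%.

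- Normal approximation: n = (7 × (1.960 + 1.282) / 1)² = 514.9, so 515.
- Paired t-test with the noncentral t distribution: n = 517 (power 0.9001), as stated.
- Withdrawal of 15%: 517 / 0.85 = 608.2, stated as 608.

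**Step 3: how much lost recording equals the planned effect.** Let B be the true rate, unchanged by the switch, and u the fraction of episodes that an on-Tresiba diary misses but a baseline diary would catch. Then:

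- apparent fall = u × B
- apparent rate ratio = 1 − u

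The protocol states no baseline rate, so B is assumed over a range. Setting u × B = 1 gives u = 1/B:

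| Assumed B (episodes/PYE) | u giving a fall of 1 | Apparent rate ratio |
|---|---|---|
| 5 | 20% | 0.80 |
| 10 | 10% | 0.90 |
| 20 | 5% | 0.95 |
| 50 | 2% | 0.98 |

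**Step 4: what a spurious fall does to the test.** With n = 517 and SD 7, SE = 7/√517 = 0.308. An observed fall of 1.96 × 0.308, about 0.60 episodes/PYE, already reaches p < 0.05. With no true change:

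- Spurious fall of 0.5, SD 7: chance of a significant reduction 0.37.
- Spurious fall of 1, SD 7: 1 − Φ(1.96 − 1/0.308) = 0.90. This is the design power restated, since the spurious shift equals the planned difference.
- Spurious fall of 1, SD 14: SE = 0.616, and the chance is 1 − Φ(1.96 − 1/0.616) = 0.37.

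A larger SD makes a significant result less likely but leaves the bias unchanged. The calculation uses the paired-difference test on which the study was sized. The regression model foreseen in 8.7.2.1 would face the apparent rate ratio of 1 − u instead.

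**The case against.** The strongest reply is that the point rests on one clause about material whose content is not shown. A reader might infer that this is the only written material patients receive about recording, or that it says nothing of later diaries. The documents support neither. The footnote names a purpose, not the full content, and 8.4.3 also provides for complete oral and written study information, which is not shown. The footnote may also serve mainly to explain why the switch waits four weeks, since the sentence before it concerns the safety of staying on current medication. This stands as a limit on the claim. It remains true that the protocol describes such emphasis for the baseline period alone.

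A reader might also infer that on-Tresiba diaries are likely to be less complete. That goes too far. Every diary carries nearly the same instruction, the guidance in 8.4.1 is not expressly confined to baseline, and episodes are categorised from the diary at each visit (8.3.2.1). Other influences could work the opposite way. Sections 3.4 and 8.1.1 cite a recommendation for close glucose monitoring in the weeks after transfer, which could raise detection on Tresiba. Section 8.9 expects better control from baseline monitoring and diary-keeping, and separately a baseline rate that is too low. The net direction is therefore unknown.

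The figures do not measure this effect. The rates are assumed, and the losses are solved backwards from the planned difference. They show how sensitive the comparison is to any loss of recording. If the PYE denominator counts only days covered by returned diaries, wholly missing diaries drop out and only under-recording within kept diaries matters. That detail may properly sit in the SAP.

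Finally, 8.9 already concedes that without a comparator many explanations for a change cannot be ruled out. That general warning stands, but it does not name unequal recording or reduce it.

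**Conclusion.** The concern holds as a risk that the protocol creates and does not acknowledge, not as a demonstrated bias. The plan describes explanation and guidance for one side of an uncontrolled before-after comparison of self-recorded episodes, and only the plain instruction for the other.

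The size of any resulting gap cannot be derived from the document. The illustration rests on assumed true rates of 5 to 20 episodes/PYE and no true change. Under those assumptions a loss of 20% down to 5% of episodes at follow-up would account for the whole planned difference, and the higher the true rate, the smaller the loss needed. Episodes never written down cannot be recovered in the analysis, so the remedy belongs in the patient material and visit procedures. It is a cheap improvement worth making, not a fatal flaw.

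**What to change.** 1. Reword footnote 1 of Table 8-1 so that the patient material explains that all five diary periods, before visits 2, 3, 4, 5 and 6, matter equally.
2. In 8.4.3 to 8.4.5, provide the same sheet and the same brief guidance with each diary handed out at visits 1 to 5.
3. In 8.9, name unequal recording between baseline and follow-up as a limitation, and say that fuller recording at baseline would look like a fall in hypoglycaemia.

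The cost is one revised sheet, a few lines in the visit procedures and a few extra minutes at visits, with no added visit and no change to treatment. Revised patient material needs ethics review where required (8.8.2, 9.3). Patients had already been enrolled under protocol version 2.0 and this is version 5.0, so new material would reach earlier and later patients differently. The study should record which patients received which version.

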8.3 Endpoints

Data will be collected during the baseline period (4 weeks before Tresiba[®] treatment, at visits 1, and 2) and at the following time points after treatment initiation: 3 months (± 45 days), 6 months (± 45 days), 9 months (± 45 days), and 12 months (± 45 days), when available.

All safety and effectiveness assessments (interviews, questionnaires and blood samples) should be performed as part of routine clinical practice. They are generally recognised as reliable, accurate and relevant to this indication (DM in adults). The biochemical assessments, FPG, and HbA1c, will be included in the analyses if available. They will not be performed unless according to clinical practice at the site. The hypoglycaemia reporting and the PRO assessments may require some questions that are not part of standard routine care.

8.3.1 Primary endpoint

Hypoglycaemic episodes will be collected throughout the study using a 4-week patient hypoglycaemia diary (collected at visits 2, 3, 4, 5, and 6) and 6 month recall for severe hypoglycaemia (visit 1). Each episode of hypoglycaemia will be reported on a dedicated eCRF page and all severe hypoglycaemic episodes (regardless of physician's evaluation of seriousness and causality) must be reported on the AE form and the safety information form (SIF) (see Section [10](#)).

For the primary observational endpoint any hypoglycaemic episode will be recorded.

8.3.2 Secondary endpoints

8.3.2.1 Classification of hypoglycaemic episodes

At visit 1 the physician will indicate on the eCRF if his/her patient is a high dose insulin user - defined as patients requiring doses >80 U daily, and/or is prone to hypoglycaemic episodes.

Hypo-prone patients are defined as having any of the below:

1. Experienced at least 1 severe hypoglycaemic episode within the last year (according to the ADA definition, April 2013 (3))
2. Moderate chronic renal failure, defined as glomerular filtration rate $30 - 59$ mL/min/1.73 m² per CKD-Epi as specified by physician statement (or according to national reference definitions if they differ from the values stated)
3. Hypoglycaemic symptom unawareness (history of impaired autonomic responses [tremulousness, sweating, palpitations, and hunger] during hypoglycaemia)

4. For T1DM: DM duration for more than 15 years
5. For T2DM: exposed to insulin for more than 5 years

For the secondary effectiveness/safety endpoints the number of hypoglycaemic episodes within the different categories of hypoglycaemia will be reported. At each visit, the treating physician, or appropriately qualified and trained delegate, will indicate in the eCRF the category (severe, non-severe, nocturnal, during sleep, or confirmed hypoglycaemia, as defined below) of each hypoglycaemic episode, based on the information recorded in the patient diary.

Severe hypoglycaemia

Severe hypoglycaemia is an event that requires assistance of another person to actively administer carbohydrate, glucagon, or other resuscitative actions (3).

These episodes may be associated with sufficient neuroglycopenia to induce seizure, unconsciousness or coma. Plasma glucose (PG) measurements may not be available during such an event, but neurological recovery attributable to the restoration of PG to normal is considered sufficient evidence that the event is induced by a low PG concentration.

The definition of severe symptomatic hypoglycaemia includes all episodes in which neurological impairment is severe enough to prevent self-treatment and which are thus thought to place patients at risk of injury to themselves or others.

All severe hypoglycaemic episodes (regardless of physician's evaluation of seriousness and causality) must be systematically reported as safety information.

Non-severe hypoglycaemia

Non-severe hypoglycaemia is an event in which the patient is able to treat themselves and includes:

- a) an event during which typical symptoms of hypoglycaemia are accompanied by a measured PG concentration ≤ 3.9 mmol/L (70 mg/dL)

OR

- b) an event during which symptoms of hypoglycaemia are not accompanied by a PG determination, but is presumably caused by a PG concentration ≤ 3.9 mmol/L (70 mg/dL); symptoms treated with oral carbohydrate without a test of PG, glucagon or intravenous glucose, and leading to a significant improvement or prompt recovery

OR

- c) an event not accompanied by typical symptoms of hypoglycaemia but with a measured PG concentration ≤ 3.9 mmol/L (70 mg/dL)

Clinical symptoms that are considered to result from a hypoglycaemic episode include increased sweating, nervousness, asthenia/weakness, tremor, dizziness, increased appetite, palpitations, headache, sleep disorder, confusion, seizures, unconsciousness, or coma.

A distinction will be made between day-time hypoglycaemia, either severe or non-severe, occurring during the waking period and nocturnal hypoglycaemia.

Nocturnal hypoglycaemia

Nocturnal hypoglycaemia is defined as any hypoglycaemia (defined by time of the day) that occurs between 00:01 and 05:59 hours, regardless of whether the patient is awake or wakes up because of the event.

Hypoglycaemia during sleep

Any hypoglycaemia occurring during sleep (defined by time of the day) of the above categories that occurs between 22:01 and 07:59 hours, that results in the patient being woken up because of the event.

Novo Nordisk definition of hypoglycaemia

Confirmed hypoglycaemic episodes are defined as severe hypoglycaemia and/or a measured PG value of <3.1 mmol/L:

- Total hypoglycaemia (severe or blood glucose confirmed) is defined as episodes that are severe and/or blood glucose confirmed by a PG value of <3.1 mmol/L (56 mg/dL), with or without symptoms consistent with hypoglycaemia.
- Severe or blood glucose confirmed symptomatic hypoglycaemia is defined as episodes that are severe and/or blood glucose confirmed by a PG value of <3.1 mmol/L (56 mg/dL), with symptoms consistent with hypoglycaemia.
- Severe hypoglycaemia is defined according to the ADA classification as stated below.

ADA classification of hypoglycaemia

- Severe hypoglycaemia: An episode requiring assistance of another person to actively administer carbohydrate, glucagon, or take other corrective actions. PG values may not be available during an event, but neurological recovery following the return of PG to normal is considered sufficient evidence that the event was induced by a low PG concentration.
- Asymptomatic hypoglycaemia: An episode not accompanied by typical symptoms of hypoglycaemia, but with a measured PG concentration ≤ 3.9 mmol/L (70 mg/dL).
- Documented symptomatic hypoglycaemia: An episode during which typical symptoms of hypoglycaemia are accompanied by a measured PG concentration ≤ 3.9 mmol/L (70 mg/dL)

- Pseudo-hypoglycaemia: An episode during which the person with diabetes reports any of the typical symptoms of hypoglycaemia with a measured PG concentration >3.9 mmol/L (70 mg/dL) but approaching that level.
- Probable symptomatic hypoglycaemia: An episode during which symptoms of hypoglycaemia are not accompanied by a PG determination but that was presumably caused by a PG concentration \leq 3.9 mmol/L (70 mg/dL).

